## **8.6 Reporting Procedures – Notifying the FDA**

The study sponsor is required to report certain study events in an expedited fashion to the FDA. These mandatory written notifications of adverse events are referred to as IND safety reports.

The following describes the IND safety reporting requirements by timeline for reporting and associated type of event:

- **As soon as possible but no later than 7 calendar days**  
Any adverse experience that is:
  - suspected, *and*
  - unexpected, *and*
  - fatal or life-threatening
  
- **As soon as possible but no later than 15 calendar days**  
Any adverse experience that is:
  - suspected, *and*
  - unexpected, *and*
  - serious, but not fatal or life-threatening

-or-

  - a previous adverse event that was not initially deemed reportable but is later found to fit the criteria for reporting (reporting within 15 calendar days from when event was deemed reportable).

### **Definitions:**

- **Suspected:** there is reasonable possibility that the drug caused the adverse event. For the purposes of IND safety reporting, 'reasonable possibility' means there is evidence to suggest a causal relationship between the drug and the adverse event.
- **Unexpected:** refers to an event or reaction that is not listed in the investigator's brochure or is not listed at the specificity or severity that has not been observed / is not consistent with the risk information described in the IND application.
- **Life-threatening:** the sponsor determines that adverse event or suspected adverse reaction is considered life-threatening if its occurrence places the participant at immediate risk of death.

**Note:** Serious adverse events related to COVID-19 infections will not be reported to the FDA unless it meets the criteria above. There is a plethora of adverse events expected in the patient population being evaluated that will be related to the COVID-19 infection and not associated with the use of bardoxolone methyl. These adverse events include death, which is expected in severe cases of COVID-19.

### **Follow-up Safety Reporting**

Sponsors are also required to identify in IND safety reports all previous reports concerning similar adverse events and to analyze the significance of the current event in light of the previous reports.

### **Reporting Process**

Adverse events may be submitted on FDA Form 3500A (MEDWATCH Form: <https://www.fda.gov/media/76299/download>), or in a narrative format. If supplied as in a narrative format, the minimum information to be supplied is noted above at the beginning of section 8.3.

CONFIDENTIAL

This material is the property of the NYU School of Medicine and Langone Medical Center. Do not disclose or use except as authorized in writing by the study sponsor

### **Study Halting Rules**

At a designated time during Phase 3 of the trial (~40% and ~70% of projected sample size has accrued) interim analysis will be performed for safety, harm and futility. Safety and harm stopping rules will be based on one-tailed group sequential Z-testing with three stages and boundaries calculated from an O'Brien-Fleming spending function. Futility stopping rules will be based on symmetric, two-tailed group sequential Z-testing with three stages and boundaries calculated from an O'Brien-Fleming spending function. The Executive Committee can request to be unblinded after receiving the recommendation from the DSMB after the Phase 2 portion of the trial. If the Phase 2 portion is unblinded, participants enrolled during Phase 2 portion will not be included in the total for the Phase 3 portion of the trial, which will require an additional 400 patients to be enrolled. If Phase 2 portion remains blinded, an additional 360 patients will be enrolled. Detailed plans for interim monitoring will be documented in a separate DSMB analysis plan.

### **8.7 Safety Oversight**

It is the responsibility of the Principal Investigator to oversee the safety of the study at his/her site. This safety monitoring will include careful assessment and appropriate reporting of adverse events as noted above, as well as the construction and implementation of a site data and safety-monitoring plan. Medical monitoring will include a regular assessment of the number and type of serious adverse events. All study information will be communicated between the PI and study sites on an as-needed basis via emails, phone calls, teleconferences, webinars, and in-person meetings. All attempts will be made to ensure communications are timely with respect to the topic of the communication.

Safety oversight will be under the direction of the NYU Langone Health COVID-19 DSMB. This DSMB committee will be comprised of individuals with expertise across a broad range of disciplines. The DSMB will operate under the rules of an approved charter. The DSMB charter will specify the meeting frequency when safety data on each arm of the study will be assessed.

## **9 Clinical Monitoring**

Clinical site monitoring is conducted to ensure that the rights and well-being of human subjects are protected, that the reported trial data are accurate, complete, and verifiable, and that the conduct of the trial is in compliance with the currently approved protocol/amendment(s), with GCP, and with applicable regulatory requirement(s).

- Monitoring for this study will be performed by designated staff at the Coordinating Center at NYU Langone Health.
- Monitoring will be performed centrally at specified time points throughout the study. For-cause on-site monitoring will be performed when needed. A random review of certain data points related to endpoint, safety, and other key data variables will be performed. Monitoring related to protocol adherence will be performed on an ongoing basis.
- Details of clinical site monitoring will be documented in a CMP. The CMP will describe the frequency of monitoring, which data points will be monitored, and the distribution of monitoring reports.

## **10 Statistical Considerations**

### **10.1 Statistical and Analytical Plans (SAP)**

A formal SAP detailing the analyses will be developed and finalized prior to database lock and unblinding of the study. All statistical analyses and data summaries will be performed using SAS® (Version 9.4 or higher) or other validated software. The SAP will serve as the final arbiter of all statistical analyses.

CONFIDENTIAL

This material is the property of the NYU School of Medicine and Langone Medical Center. Do not disclose or use except as authorized in writing by the study sponsor

## **10.2 Statistical Hypotheses**

### **10.2.1 Phase 2**

In a given group of 20 subjects the probability of not observing an adverse event when the underlying rate is 10%, 20%, 30%, 40%, and 50% is 0.12, 0.01, 0.001, 0, and 0, respectively. This indicates that in a sample of 20 subjects, the study is sufficiently sized to observe AEs that occur at a rate of 10% or greater.

### **10.2.2 Phase 3**

All statistical hypotheses will be tested using a two-sided significance level of 0.05. The Phase 3 primary outcome is recovery at Day 29. The key parameter of interest is the “risk difference,” which quantifies the shift in probability of recovery resulting from treatment. A positive risk difference 1 indicates a higher proportion of patients recovering in the bardoxolone methyl group relative to placebo. The null hypothesis to be tested is that the risk difference is the same for the placebo and bardoxolone methyl arms and is stated as  $H_0: RD = 0$ , where RD denotes the risk difference.

## **10.3 Analysis Populations**

The following analysis populations will be defined:

- The intention-to-treat (ITT) population includes all randomized patients categorized by their assigned treatment group (whether or not they received study drug). Efficacy analyses of the primary and secondary outcomes will be performed using the ITT population.
- The safety population includes all patients who received at least one dose of randomized study drug. Patients who receive at least one dose of bardoxolone methyl will be classified in the bardoxolone methyl group, and patients who receive at least one dose of placebo and no dose of bardoxolone methyl will be classified in the placebo group.
- Additional analysis populations may be defined in the SAP as appropriate.

## **10.4 Description of Statistical Methods**

The following subsections include brief descriptions of the planned statistical methods. Full detail of the planned analyses will be described in the formal SAP.

### **10.4.1 General Approach**

This is a double-blind placebo controlled randomized trial testing a superiority hypothesis with a two-sided significance level of 0.05. Data for this placebo-controlled trial will be summarized by treatment group using descriptive statistics. Continuous data will be summarized with number of patients (n), mean, median, minimum, maximum, relevant quartiles, standard deviation, coefficient of variation, and geometric mean (where applicable). Categorical data will be summarized using frequency counts and percentages. Handling of missing data will be described in the SAP.

### **10.4.2 Analysis of the Phase 3 Primary Efficacy Endpoint**

The primary efficacy endpoint is recovery, where recovery is defined as meeting all of the following criteria at Day 29:

- Alive,
- Free of respiratory failure, and
- Free of renal replacement therapy (RRT).

Analysis of the Phase 3 primary endpoint will occur after the last patient enrolled has been followed up to Day 29 and the study is complete. The analysis will be based on the test of treatment effect estimated from a generalized linear model analysis accounting for the stratification factors of study center and mechanical ventilation status as covariates. The primary efficacy endpoint will be a covariate-adjusted estimate as specified in the Statistical Analysis Plan. Events will be analyzed and presented as summary tables of proportion recovered with risk differences and 95% confidence intervals (CIs) for the comparison of

CONFIDENTIAL

This material is the property of the NYU School of Medicine and Langone Medical Center. Do not disclose or use except as authorized in writing by the study sponsor

bardoxolone methyl to placebo. The SAP will include additional detail of the planned analyses and definitions of sensitivity analyses.

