##### 7.1.1.3 Demographics and Baseline Disease Characteristics

Demographic data including sex, age, race, and ethnicity, will be collected as indicated in [Table 1](#). Baseline disease characteristics will be collected as indicated in [Table 1](#).

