## 10.5 Sample Size

A total sample size of approximately 400 participants (Phase 2 combined with Phase 3, or Phase 3 alone, depending on unblinding of Phase 2) randomized 1:1 using block randomization (~200 bardoxolone methyl; ~200 placebo) is expected to provide approximately 80% power at a two-sided 0.05 significance level using a generalized linear model analysis to detect a risk difference of +.14, assuming the following:

- Follow-up for events for 28 days after randomization (at Day 29)
- 2% of patients in each group drop-out prior to Day 29
- Increase in the probability of recovery from 50% for patients randomized to placebo relative to 64% of patients randomized to bardoxolone methyl.

Under these assumptions, approximately 228 (57% of the 400 enrolled) will have recovered at Day 29. The primary analysis will be based on the ITT population. The secondary endpoints will be tested using a strategy that preserves the overall Type I error rate. Analysis of the primary endpoint will occur after the last patient enrolled has been followed to Day 29. The phase 2 analysis for safety will not assess the primary endpoint and will not impact the overall type I error rate of the trial. If the DSMB concludes the trial should continue to the Phase 3 part, then the phase 2 patients will be included in the phase 3 portion of the study.

Table 5 shows effects detectable with 80% power for a total sample size of 400 and a range of proportion of placebo patients recovered at Day 29.

**Table 5. Effects detectable with 80% power for a sample size of n=400 and a range of proportion of placebo patients recovered**

Placebo Proportion Recovered at Day 29	Bardoxolone Proportion Recovered at Day 29	Risk Difference
0.350	0.488	0.14
0.400	0.539	0.14
0.450	0.590	0.14
0.500	0.638	0.14
0.550	0.686	0.14
0.600	0.732	0.13
0.650	0.776	0.13
0.700	0.819	0.12
0.750	0.861	0.11
0.800	0.900	0.10
0.850	0.936	0.09
0.900	0.969	0.07

CONFIDENTIAL

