## **10.6 Measures to Minimize Bias**

### **10.6.1 Enrollment/Randomization/Masking Procedures**

An IWRS will be utilized to randomize patients 1:1 to once daily administration of bardoxolone methyl or placebo. Randomization will be performed using block randomization with the following strata: center and invasive mechanical ventilation (i.e., mechanical ventilation with endotracheal intubation) at baseline (yes or no). Enrollment of patients  $\geq 70$  years of age may be limited (e.g., comprise no more than 10% of all randomized patients), pending safety review by the DSMB and executive committee

All patients, investigators, site personnel, laboratories, and study personnel with direct involvement in the conduct of the study or their designees will be blinded to treatment assignments. To prevent potential bias, appropriate measures will be taken to ensure the blind is maintained for the patients and personnel mentioned previously. To maintain the blind, investigators will distribute blinded study drug treatment to patients as directed by the IWRS system. Investigators and patients will not be blinded to dose level, but will be blinded to treatment assignment (i.e., bardoxolone methyl vs. placebo).

An IWRS will manage treatment assignments and study drug dispensing. The only people with direct access to treatment assignments prior to database lock will be those individuals who develop and maintain the randomization code and the DSMB.

Following database lock after completion of each phase the study, randomization codes will be released to the statistical team for analysis.

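### The primary model names only center and ventilation as covariates; adding age and baseline eGFR would probably bring a modest gain in precision, of a size the documents cannot fix

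*Combined protocol and SAP*

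**What the plan says.** Section 10.4.2 bases the primary test on a treatment effect from a generalized linear model "accounting for the stratification factors of study center and mechanical ventilation status as covariates". The next sentence says that the result will be covariate-adjusted as the SAP specifies, and the section leaves further detail to the SAP. Section 10.4 calls its subsections brief. Section 10.1 makes the SAP decisive and requires it to be final before database lock and unblinding. That SAP is not in the documents.

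Both candidate covariates will be in the dataset:

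- **Age.** Section 7.1.1.3: "Demographic data including sex, age, race, and ethnicity, will be collected".
- **Baseline eGFR.** Section 7.1.1.13 computes it by CKD-EPI from creatinine, age, sex and race. The Schedule of Assessments (Section 19) has a metabolic panel at screening and pre-dose on Day 1. Section 5.2 excludes eGFR below 30, so a value is needed to judge eligibility.

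Age is not a randomization stratum. Section 10.6.1 stratifies by center and invasive ventilation. It adds that enrollment at age 70 and over may be limited, the example being that they "comprise no more than 10% of all randomized patients), pending safety review by the DSMB and executive committee".

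**The concern.** Recovery at Day 29 requires a patient to be alive, free of respiratory failure and free of renal replacement therapy. Age and kidney function at entry are natural candidates to predict those components, and the plan itself singles out older patients for a possible enrollment limit. If they do predict recovery, adjusting for them reduces the variance of the estimated risk difference and leaves its target unchanged. The design aims for about 80% power, so a few points would be worth having when no new data need to be collected.

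**Working it through.** **Inputs from the documents.** Section 10.2.2: "All statistical hypotheses will be tested using a two-sided significance level of 0.05". Section 10.5: "A total sample size of approximately 400 participants", "randomized 1:1 using block randomization", which "is expected to provide approximately 80% power at a two-sided 0.05 significance level". The assumed effect is "Increase in the probability of recovery from 50% for patients randomized to placebo relative to 64% of patients randomized to bardoxolone methyl", with 2% dropout per group. Section 5.6 plans about 20 sites.

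**Step 1: reproduce the stated size.** With p0 = 0.50, p1 = 0.64 and mean 0.57, the pooled two-proportion formula without continuity correction is

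n = [1.96·√(2·0.57·0.43) + 0.8416·√(0.50·0.50 + 0.64·0.36)]² / 0.14²
= [1.372 + 0.583]² / 0.0196 ≈ 195.1, so 196 per arm.

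Total 392; 392 / 0.98 = 400. Power at 196 per arm is 80.2%. The plan's figure is met by an unadjusted test, with no credit for any covariate.

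**Step 2: what prognostic adjustment could add.** If the added covariates explain a share R² of outcome variance, the effective n per arm is about 196 / (1 − R²). The total for 80% power is 392·(1 − R²) / 0.98. The 95% CI half-width is 1.96·√(0.4804 / n_eff). The documents give no R², so a range is shown.

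| R² | Power | Total N for 80% | CI half-width |
|---|---|---|---|
| 0 | 80.2% | 400 | 0.097 |
| 0.02 | 81.0% | 392 | 0.096 |
| 0.05 | 82.2% | 380 | 0.095 |
| 0.10 | 84.2% | 360 | 0.092 |
| 0.20 | 88.1% | 320 | 0.087 |

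**Step 3: age alone, by simulation.** The model was logistic with standardization, for 392 patients, 15% ventilated, with 20 centers grouped into 4 regions. The ventilated share, the grouping and the age effects are assumptions. There were 3,000 trials per setting under the alternative.

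| Log-odds per SD of age | Power without age | Power with age | Gain (points) |
|---|---|---|---|
| 0.3 | 83.6% | 84.1% | 0.5 |
| 0.5 | 84.0% | 85.4% | 1.4 |
| 0.7 | 83.6% | 87.2% | 3.6 |

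Type I error with age in the model was 5.1% (5,000 null trials). The Monte Carlo SE of each power figure is about √(0.84·0.16 / 3000) = 0.7 points, so the smallest gain is not clearly separate from noise.

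**Step 4: age and eGFR together, by simulation.** 1,000 trials per setting, 392 patients, ventilation already in the model. Assumed: mean age 58 (SD 14), eGFR falling with age, 15% ventilated, ventilation odds ratio 4, no center effects. Each cell gives the result without, then with, a 10% cap on patients aged 70 or over.

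| OR per 10 years; per 15 eGFR units | Variance ratio | Power gain (points) |
|---|---|---|
| 1.0; 1.0 | 1.005; 0.998 | 0.6; 0.0 |
| 1.2; 1.1 | 0.968; 0.963 | 2.4; 1.0 |
| 1.5; 1.2 | 0.911; 0.880 | 4.7; 4.9 |
| 2.0; 1.3 | 0.822; 0.847 | 7.7; 6.0 |

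Monte Carlo error is about 1.2 points on each power figure; the 0.6 in the first row is noise. The cap lowered the total variance explained, from 0.145 to 0.132 in the third setting and from 0.251 to 0.225 in the fourth.

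**Step 5: size of a chance age imbalance.** With 196 per arm, one standard error of the difference in mean age is √(2/196) = 0.10 SD. At 0.5 log-odds per SD it shifts the unadjusted risk difference by about 0.10 × 0.5 × 0.245 = 0.012, or 1.2 points against a 14-point target. The standard error already allows for such shifts.

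**The case against.** The strongest reply is that nothing has been left out. Section 10.4.2 defers the adjusted estimate to a SAP that the reader cannot see, and that SAP may well list age and eGFR. This stands: the documents show two covariates named and the final list deferred, not two variables rejected.

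It is also fair that the documents do not quantify prognostic value. The possible limit at age 70 awaits a safety review and is not evidence of prognostic strength. The kidney-injury figures in Section 2.1 concern injury during COVID-19, not kidney function at entry. An age cap, the eGFR exclusion and the age term inside CKD-EPI would all tend to shrink the gain.

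Three stronger readings are tempting, and the documents support none of them:

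- **That age imbalance biases the result.** Under randomization it is variance, already reflected in the standard error and the type I error.
- **That the trial is underpowered without these covariates.** Step 1 reaches 80.2% with none.
- **That the gain is free.** About 20 centers by 2 ventilation strata gives up to 40 cells, averaging 400 / 40 = 10 patients. Section 10.4.2 does not state the link. With an identity link, more covariates could worsen convergence. The baseline eGFR is also not defined between the screening and Day 1 values.

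Deferral does not make the point idle. Section 10.6.1 releases randomization codes to the statistical team after database lock of each phase, and Section 10.5 carries Phase 2 patients into the Phase 3 analysis. Section 8.6 drops them only if Phase 2 is unblinded. Section 10.1 does not say which lock closes the SAP, so the covariate list could still be open when codes for some primary-analysis patients are in hand.

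**Conclusion.** The point holds as a missed efficiency. The only covariates named for the primary model are the two stratification factors, while two plausible predictors will be on file before dosing. The planned test is valid and the stated power stands.

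The gain depends wholly on assumed prognostic strength: about 0.5 to 3.6 power points for age alone over the range in Step 3, up to about 8 points for age and eGFR together if both are strong, and none if neither predicts recovery. Neither simulation fitted the roughly 20 individual centers that Section 10.4.2 implies, so the figures show order of magnitude only.

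**What to change.** In Section 10.4.2 or the SAP, before any treatment-coded data are released to the statistical team:

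1. Add age (continuous) and baseline eGFR (continuous, last pre-dose value) to the primary model, alongside ventilation and center.
2. Estimate the risk difference by standardization from a logistic model, so that added covariates do not cause identity-link convergence failure, and name the standard error.
3. State how small centers are handled in the model.
4. State how missing covariate values are handled.

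The cost is a few lines of text and slightly more modelling work, with no new data collection. The gain may turn out to be small.

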### **10.4.3 Analysis of the Secondary/Exploratory Endpoints**

The secondary endpoints include the following:

- Change in eGFR (mL/min/1.73 m^2) during treatment as calculated using the CKD-EPI formula.
- Number of mechanical ventilation-free days.

The two treatment groups will be compared with respect to the secondary endpoints. The treatment of missing data, and the strategy to preserve the overall Type I error will be described in the SAP.

### **10.4.4 Safety Analyses**

Safety and tolerability are evaluated by AEs, SAEs, clinical laboratory test results, vital sign measurements, and PaO2/FiO2 ratio. All analyses of the safety data will be performed using the safety analysis set. Descriptive statistics are presented by treatment group assignment in the safety analysis set.

#### **10.4.4.1 Adverse Events**

The Medical Dictionary for Regulatory Activities (MedDRA) dictionary will be used to classify all AEs reported during the study by system organ class (SOC) and preferred term (PT). All summary tables will include counts of patients with treatment-emergent adverse events (TEAEs). TEAEs are defined as those AEs that have an onset time either at or after the start of study drug administration and no more than 30 days after the last dose of study drug is administered. An overall summary of TEAEs will be presented with the number and percentage of patients having a TEAE, a serious TEAE, a TEAE leading to study discontinuation, a TEAE with an outcome of death, a TEAE related to study drug (definitely, probably, or possibly related), or a severe TEAE. The overall incidence of TEAEs will be summarized by SOC and by SOC and PT using the number and percentage of patients reporting an event and the number of events reported. The incidence of serious TEAEs and TEAEs leading to premature study discontinuation will be summarized in a similar manner. TEAEs will also be summarized by maximum severity (mild, moderate, or severe), and assessed relationship to study drug with the percentage of patients in each category. TEAEs leading to premature study discontinuation, and TEAEs with an outcome of death will also be presented in separate listings.

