### 7.2.1 Screening/Enrollment

#### Screening/Enrollment Visit (Day -3 to 1)

- Obtain informed consent of potential participant, or legally authorized representative verified by signature on study informed consent form. Written and/or electronic signature are acceptable.
- Review medical history and medications history to determine eligibility based on inclusion/exclusion criteria.
- Perform medical examinations needed to determine eligibility based on inclusion/exclusion criteria.
- Verify inclusion/exclusion criteria.
- Obtain blood or urine for pregnancy test if subject is WOCBP.
- Obtain demographic information, medical history, medication history, alcohol and tobacco use history.
- Review and record vital signs, results of medical examinations, results of laboratory assessment, and other assessments as indicated in [Table 1](#).

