#### **8.1.1 Definition of Adverse Events (AE)**

An **adverse event** (AE) is any symptom, sign, illness or experience that develops or worsens in severity during the course of the study. Intercurrent illnesses or injuries should be regarded as adverse events. Abnormal results of diagnostic procedures are considered to be adverse events if the abnormality:

CONFIDENTIAL

This material is the property of the NYU School of Medicine and Langone Medical Center. Do not disclose or use except as authorized in writing by the study sponsor

- results in study withdrawal
- is associated with a serious adverse event
- is associated with clinical signs or symptoms
- leads to additional treatment or to further diagnostic tests
- is considered by the investigator to be of clinical significance

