### 8.3 Time Period and Frequency for Event Assessment and Follow-Up

The occurrence of an AE or SAE may come to the attention of study personnel during study visits and interviews of a study participant presenting for medical care, or upon review by a study monitor. All adverse events will be captured on the appropriate eCRF. Information to be collected includes event description, time of onset, clinician's assessment of severity, relationship to study product (assessed only by those with the training and authority to make a diagnosis), and time of resolution/stabilization of the event. All AEs will be followed to adequate resolution.

Any medical condition that is present at the time that the participant is screened will be considered as baseline and not reported as an AE. However, if the study participant's condition deteriorates at any time during the study, it will be recorded as an AE. UPs will be recorded in the data collection system throughout the study.

Changes in the severity of an AE will be documented to allow an assessment of the duration of the event at each level of severity to be performed. AEs characterized as intermittent require documentation of onset and duration of each episode.

The PI will record all reportable events with start dates occurring any time after informed consent is obtained until 7 (for non-serious AEs) or 30 days (for SAEs) after the last day of study participation. At each study visit, the investigator will inquire about the occurrence of AE/SAEs since the last visit. Events will be followed for outcome information until resolution or stabilization.

CONFIDENTIAL

This material is the property of the NYU School of Medicine and Langone Medical Center. Do not disclose or use except as authorized in writing by the study sponsor

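### The TEAE definition has no worsening clause, so an event that starts between consent and first dose and worsens on study drug can be missed in the TEAE tables

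*Combined protocol and SAP*

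**What the plan says.** Section 10.4.4.1 sets the counting rule: "TEAEs are defined as those AEs that have an onset time either at or after the start of study drug administration". The counting window closes 30 days after the final dose. The summaries listed there all count TEAEs: overall, by system organ class and preferred term, serious, related, severe or by maximum severity, leading to study discontinuation, and with an outcome of death.

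The definition of an adverse event in section 8.1.1 is wider: "any symptom, sign, illness or experience that develops or worsens in severity during the course of the study". Section 8.3 covers reportable events "with start dates occurring any time after informed consent is obtained", and section 7.2.1 places the screening and consent visit between Day -3 and Day 1. Section 8.3 adds: "Changes in the severity of an AE will be documented", so that time spent at each level of severity can be assessed. It treats a condition present at screening as baseline, and makes a later deterioration an adverse event.

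Other places start the clock later. Section 7.2.2.1 (Visit 1) and section 8.4.1 (SAE reporting) start at the first dose. The Schedule of Assessments (section 19, Table 1) has no adverse event mark at screening. Its footnote places the Day 1 assessment after dosing and limits collection to serious events with a reasonable possibility of a relation to study drug.

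**The concern.** An adverse event includes worsening, but a TEAE requires a post-dose onset. Where the two differ, an event can deteriorate on study drug and still fail the counting rule because it began before the first dose.

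This matters because safety is the Phase 2 primary endpoint (section 4.2.1.1), with frequency and intensity of serious events named, and a Phase 3 primary objective (section 3.2.1). The population is hospitalised, and section 2.3 describes rapid progression to serious complications. Worsening of something already under way is a plausible form for drug harm to take here. If such cases drop out, the serious, severe and fatal TEAE counts are too low, and similar cases may be counted at one site and not at another.

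**Working it through.** There is no stated figure to reproduce, because the point turns on wording. I set the rules side by side and followed one case through them.

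1. **Counting rule (10.4.4.1).** Count if onset is at or after first dose and no later than last dose + 30 days. Grade, seriousness and outcome do not enter the rule.
2. **Recording rule (8.3).** The record may start at consent. Severity changes are documented for the existing event. No section says that a change of severity creates a new onset date.
3. **Exposed window (7.2.1).** From consent, as early as Day -3, to first dose on Day 1. This is a few days at most, and nothing if consent and dosing fall on the same day.
4. **Illustrative case (days and grades are mine).** Consent Day -2; grade 2 event starts Day -1; first dose Day 1; event reaches grade 4 on Day 5.
   - *One record, original start date.* Onset Day -1 is before Day 1, so it is not a TEAE. It is absent from the serious and severe counts, and from the fatal count if the patient then dies of it.
   - *Deterioration entered as its own event.* Onset Day 5 is after Day 1, so it is a TEAE and is counted.
   - *Collection starts only at first dose (7.2.2.1, 8.4.1, Schedule of Assessments).* No pre-dose record need exist. If the Day 5 deterioration is entered as a new event, it counts.

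   The same clinical course is counted or not according to site practice, across about 20 sites (section 5.6).
5. **Outputs that do not use the rule.** Laboratory results, vital signs and PaO2/FiO2 (10.4.4); unexpected deaths (8.1); all-cause mortality at Day 29 (4.2.2.2) in all randomized patients (10.3).
6. **Size, by assumption only.** Patients affected = N × p × d. Here p is the share of patients with an event that starts in the window and worsens after dosing, and d is the share of those kept under the pre-dose date. The documents give neither. Take p from 0.5% to 5% and d = 1, the worst case:
   - N = 400: 400 × 0.005 = 2, to 400 × 0.05 = 20.
   - N = 40 (Phase 2): 40 × 0.005 = 0.2, to 40 × 0.05 = 2.

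   With d = 0 the loss is zero. These figures scale the problem and do not estimate it.

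**The case against.** The strongest reply is that the gap may hardly exist. Worsening is part of the adverse event definition, section 8.3 makes deterioration an adverse event, and several places begin collection at or after first dose. If sites work that way, there is no pre-dose record for the rule to exclude. This stands as far as it goes: exclusion is possible, not certain. But section 8.3 says the opposite about when recording starts, and its deterioration sentence follows the one on conditions present at screening and gives no dating rule.

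A second reply is that sections 10.1 and 10.4 leave full detail to a formal SAP, which is not part of the document reviewed. That SAP could add a dating rule. Even so, section 10.4.4.1 states its definition as settled, so the SAP would have to change it and not merely elaborate it.

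A reader might also infer more than the text supports:
- **That these events vanish from every safety output, deaths included.** They do not; step 5 of the working lists what is untouched. Those outputs are only a partial substitute. The laboratory and physiological summaries carry no seriousness or causality, section 8.2.3 lists death among expected COVID-19 events, and all-cause mortality is an efficacy endpoint without attribution.
- **That raised transaminases within the entry limit of 5 times ULN, or respiratory disease at entry, are lost.** These are conditions present at screening. Section 8.3 makes their deterioration an adverse event, and it is counted if dated from the deterioration.
- **That a difference between the arms is hidden.** No rate, overall or by arm, is given from which to derive one.

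**Conclusion.** The point holds in limited form. The onset-only rule allows an adverse event that starts after consent and before first dose to stay out of all TEAE-based tables, including serious, severe and fatal TEAEs, even though it worsens on study drug. This rests on two conditions: that recording begins at consent, as section 8.3 says, and that the site keeps the original start date. The number of patients is unknown and probably small, because the window is so short. The definition is still worth correcting: safety is a primary concern in both phases, the rule is narrower than the protocol's own concept of an adverse event, and the change is cheap.

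**What to change.** - **Definition (10.4.4.1).** Define a TEAE as an adverse event that starts, increases in CTCAE grade, or becomes serious or fatal at or after first dose and within the existing 30-day window. Tabulate it at its highest post-dose grade and outcome.
- **Dating rule.** State that a post-dose deterioration of a condition present before dosing takes the date of deterioration as its onset.
- **Start of recording.** Reconcile section 8.3 (consent) with sections 7.2.2.1 and 8.4.1 and the Schedule of Assessments with its footnotes (first dose or after dosing). Without this the first change may not work: if pre-dose events and their grades are not collected, there is no baseline grade against which to detect worsening. The footnote limiting collection to serious, possibly drug-related events needs the same attention, since an event before the first dose could hardly meet it.

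The cost is one sentence, a derivation rule that uses the severity changes section 8.3 already asks sites to document, and aligned wording on when recording starts. The downside is that some worsening due to COVID-19 itself will be counted, but under the same rule in both arms. The formal SAP should carry the same definition and be final before unblinding, as section 10.1 already requires.
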